#### Schema

Primary endpoint: PFS; 90% power to detect difference between 4.5 months for control vs. 7.65 months for experimental arm ( $\alpha$  = 0.10,  $\beta$  = 0.10)

\* Treatment should not be started until at least 28 days after last bevacizumab dose.

Rev. 6/14 \*\* Arm B closed to accrual in Addendum #5. New patients are randomized to Arm A or Arm C.

Rev. 6/14 Accrual Goal = 135

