#### Primary Efficacy Design

Patients will be randomized equally between the two treatment arms A (IC) and C (mICR) with stratification based on performance status (0 vs. 1), discontinuation of oxaliplatin before disease progression (Yes vs. No), and time frame of progression (within 6 months of last treatment vs. > 6 months since last treatment). Patients previously randomized to arms A and B before the redesign of the experimental regimen will not be part of the formal efficacy evaluation and will be reported separately.

With 48 eligible patients per arm followed for progression-free survival (disease progression or death without evidence of progression), this study has over 85% power to detect a difference of 4.5 months median PFS in the control arm A (40% PFS at 6 months assuming exponential failure) versus 7.65 months median PFS (58% PFS at 6 months) in the experimental arm (Arm C) using a one-sided stratified log rank test conducted with 15% type 1 error. The study will require approximately 10 months of accrual at 10 patients per month and 6 additional months of follow-up to achieve the events required (67 PFS events) to provide at least 85% power for the stated alternative of a 48% increase in median PFS. Response, overall survival, and toxicity are secondary endpoints and will be reported at the time of primary PFS analysis. With 48 eligible patients per arm, the width of any 90% confidence interval on a binomial proportion will be no wider than 26 percentage points. In addition, the probability of observing a rare (2% probability) toxicity in either arm is greater than 62% at full accrual. Allowing for roughly 5% ineligibility and including the 35 patients who were previously randomized to Arms A and B of the study prior to its redesign, this study will require a total of 135 patients and 100 patients will be accrued to the revised study (Arm A versus Arm C).

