This study will be monitored by the ECOG-ACRIN Data Safety Monitoring Committee (DSMC) for early stopping due to efficacy and futility. One interim stratified log rank test for efficacy will be performed at 60% PFS information (40 PFS events), expected to occur roughly at the time accrual completes and six months before full information is achieved. Type I error control will be accomplished using an O'Brien-Fleming type boundary, with Lan-Demets use function methodology to adjust the boundary for the exact information time achieved at the interim analysis. If the study is positive, the DSMC may recommend early reporting; there is at least 55% probability of rejecting the null at the interim analysis if the alternative hypothesis is true. At the interim analysis time, the PFS hazard ratio will also be computed from a stratified proportional hazards regression model. If the HR exceeds 1 (that is, evidence that PFS is worse in the experimental Arm C), the DSMC may recommend abandoning the regimen and early reporting of negative results. The effect of the interim analysis Rev. 6/14

Rev. 12/11

on the operating characteristics of the trial is fairly small (less than 1% absolute effect on significance level and power).

Additional Safety Monitoring

In addition to the safety monitoring that will occur in the first 16 patients randomized to Arm C (described above), interim analyses of toxicity are performed twice yearly for all ECOG-ACRIN studies. Reports of these analyses are sent to the ECOG-ACRIN Principal Investigator or Senior Investigator at the participating institutions. Expedited reporting of certain adverse events is required, as described in Section 5.2 and ECOG-ACRIN Operations Office – Boston's real-time monitoring of events through CTEP-AERS report notifications will be in place for this trial. This system provides monthly notifications to the study chair, study statistician and independent toxicity monitor of certain reportable grade 4 or higher events and all grade 5 events.

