# Rev. 6/14 9.2 Original Statistical Design (Arms A and B)

Patients will be randomized equally between the two treatment arms with stratification based on performance status (0 vs. 1), discontinuation of oxaliplatin before disease progression (Yes vs. No), and time frame of progression (within 6 months of last treatment vs. > 6 months since last treatment). With 70 eligible patients per arm followed for progression-free survival (disease progression or death without evidence of progression), this study has 90% power to detect a difference of 4.5 months median PFS in the control arm (40% PFS at 6 months assuming exponential failure) versus 7.65 months median PFS (58% PFS at 6 months) in the experimental arm using a one-sided log rank test conducted with 10% type 1 error. The study will require approximately 7 months of accrual at 20 patients per month and 7 additional months of follow-up to achieve the events required (100 PFS events) to provide 90% power for the stated alternative of a 70% increase in median PFS. Response, overall survival, and toxicity are secondary endpoints and will be reported at the time of primary PFS analysis. With 70 eligible patients per arm, the width of any 90% confidence interval on a binomial proportion will be no wider than 21 percentage points. In addition, the probability of observing a rare (1% probability) toxicity in either arm is greater than 50% at full accrual. Allowing for 5% ineligibility, this study will require a total of 147 patients.

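### The Schema still gives the closed A versus B design's alpha of 0.10 and 90% power; Section 9.1 runs Arm A versus Arm C at one-sided alpha 0.15 with over 85% power

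*Combined protocol and SAP*

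**What the plan says.** **Schema.** The design line names PFS as the primary endpoint and states "90% power to detect difference between 4.5 months for control vs. 7.65 months for experimental arm", with alpha 0.10 and beta 0.10. It gives no sidedness, test or event count. The notes below it, marked Rev. 6/14, say "Arm B closed to accrual in Addendum #5. New patients are randomized to Arm A or Arm C" and set the accrual goal at 135.

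**Section 9.1, the revised design for Arms A and C.** The primary comparison is made "using a one-sided stratified log rank test conducted with 15% type 1 error". With 48 eligible patients per arm, the study runs "to achieve the events required (67 PFS events) to provide at least 85% power". The medians are again 4.5 and 7.65 months. The total of 135 is 100 patients for A versus C plus the 35 randomized before the redesign, and those 35 are excluded from the formal efficacy evaluation. One efficacy interim is planned at 40 PFS events, and "there is at least 55% probability of rejecting the null at the interim analysis if the alternative hypothesis is true".

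**Section 9.2, the original design for Arms A and B.** Same medians, 70 eligible patients per arm, 147 in total, "using a one-sided log rank test conducted with 10% type 1 error", and follow-up "to achieve the events required (100 PFS events) to provide 90% power".

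**The concern.** The Schema was only partly updated. Its arms and accrual goal come from the redesign, while its alpha and power come from the design that the redesign replaced. Nothing in its text marks the design line as historical.

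The Schema is where many readers look first for the error rates. As printed, it claims a stricter test and a higher power than the A versus C comparison has. It also leaves the protocol with two prespecified alphas for what reads as one primary analysis. A result that passes at 0.15 and fails at 0.10 could then be disputed from the document itself.

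**Working it through.** **Inputs.** Medians 4.5 and 7.65 months (Schema, 9.1 and 9.2), so HR = 4.5/7.65 = 0.588 and |ln HR| = 0.5306. Allocation is 1:1. Events are 67 (9.1) and 100 (9.2). One-sided alpha is 0.15 (9.1) and 0.10 (9.2). Normal quantiles: z = 1.0364 for 0.15 and 1.2816 for 0.10.

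**Formulae (Schoenfeld).** Power = Φ(|ln HR| × √(d/4) − z_α). Required events d = 4(z_α + z_β)² / (ln HR)².

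**Step 1: reproduce the plan's own figures.**
- Section 9.1: 0.5306 × √(67/4) = 2.172, and Φ(2.172 − 1.036) = 87.2%. Freedman's formula gives 86.1%. The stated figure of over 85% holds.
- Section 9.2: 0.5306 × √(100/4) = 2.653, and Φ(2.653 − 1.282) = 91.5%. Freedman gives 90.5%. The stated 90% holds.
- Two-sided versions reproduce neither (76.8% and 84.3% by Schoenfeld), so both sections are one-sided, as they say.

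**Step 2: put the Schema's alpha on the current design.**
- 67 events at one-sided 0.10: Φ(2.172 − 1.282) = 81.3%, not 90%. Read as two-sided, it is 70.1%.
- Events needed for 90% power at one-sided 0.10: 4 × (1.2816 + 1.2816)² / 0.5306² = 93.3, so 94. Freedman gives 98. That is close to the 100 events of Section 9.2 and far above 67.

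**Step 3: check against the interim statement in Section 9.1.** Looks at 40 and 67 events give t = 40/67 = 0.597. The Lan-DeMets O'Brien-Fleming-type spending function is α(t) = 2[1 − Φ(z_{α/2}/√t)]. The expected interim z under the alternative is 0.5306 × √(40/4) = 1.678.

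| | alpha 0.15 | alpha 0.10 |
|---|---|---|
| Alpha spent at interim | 0.0625 | 0.0333 |
| Interim z (HR) | 1.535 (0.616) | 1.835 (0.560) |
| Interim rejection under the alternative | 55.7% | 43.8% |
| Final z (HR) | 1.116 (0.761) | 1.339 (0.721) |
| Final nominal one-sided p | 0.132 | 0.090 |
| Overall power | 86.4% | 80.6% |

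At alpha 0.15 the 55.7% matches the stated chance of at least 55%. The interim look costs 87.2 − 86.4 = 0.8 points of power, in line with the effect of under 1% that Section 9.1 states. At 0.10 the interim statement would be false.

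**Step 4: where the two alphas disagree.** Under this boundary, a final nominal p between about 0.090 and 0.132 (observed HR about 0.72 to 0.76) is positive under 9.1 and negative at the Schema's alpha. Under the alternative, the chance of a positive trial differs by 86.4 − 80.6 = 5.8 points.

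**The case against.** The strongest reply is that the protocol already settles the matter. The section titles label 9.1 as revised and 9.2 as original, and 9.1 gives the test, sidedness, stratification, alpha and events in full. No success threshold can be worked out from the Schema alone. Anyone who did apply 0.10 would be using a stricter test, so the false-positive risk would fall and the cost would be power. All of this is correct. It limits the consequence, but it does not make the Schema's line true.

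Three narrower points also stand:
- The conflict is in alpha and power only. The Schema gives no event count, and the medians agree in all three places.
- The p range in Step 4 depends on the boundary. It applies the 9.1 interim plan to the Schema's alpha, although 9.2, the source of that alpha, plans no efficacy interim. A classical O'Brien-Fleming boundary gives 0.087 to 0.128, and the spending form 4[1 − Φ(z_{α/4}/√t)] gives 0.095 to 0.141. With no interim look it is 0.10 to 0.15.
- The interim check supports 0.15 but depends on the same choice. The classical boundary gives 58.2% at 0.15 and 46.8% at 0.10. The second spending form gives 48.2% and 37.1%, so there neither alpha reaches 55%. Under no form does 0.10 reach it.

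The Schema's diagram is not reproduced in the text available here, so a label inside it cannot be ruled out. The visible text has none.

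**Conclusion.** The concern holds. The Schema's alpha of 0.10 and power of 90% are wrong for the A versus C comparison; they describe the closed A versus B design. The type 1 error is understated by 0.05 (0.10 against 0.15). The stated 90% compares with over 85% in Section 9.1, which works out at 86 to 87%. If alpha 0.10 were really used with 67 events, power would be about 81%.

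These figures assume proportional hazards with HR 0.588, equal allocation and the Schoenfeld approximation; the two-look figures also assume the spending function in Step 3. That Section 9.1 governs rests on its title and explicit text, with the interim statement as support. The analysis plan is not broken: the power and event counts in 9.1 and 9.2 reproduce from their stated medians. The line should be corrected because it states the trial's error rates wrongly and the correction costs almost nothing.

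**What to change.** Replace the Schema's design line with the Section 9.1 values: primary endpoint PFS, Arm A versus Arm C, median 4.5 versus 7.65 months, one-sided stratified log rank test, type 1 error 0.15, at least 85% power, 67 PFS events. If a beta is shown, 0.15 is the value that corresponds to 85% power. Keep alpha 0.10 and 90% power only in Section 9.2.

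This is a one-line amendment, best made before the primary analysis is reported. Sample size, event target, test and interim boundary stay as they are. The only drawback is that the Schema will show a less favourable alpha and power.

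When copying from Section 9.1, take the medians and not its description of the alternative as a 48% increase: 7.65/4.5 = 1.70, a 70% increase, as Section 9.2 says. That is a separate slip and does not affect this point.

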#### 1. Introduction

- 1.1 Colon Cancer
  - 1.1.1 Background

Colorectal cancer (CRC) is a significant cause of cancer mortality. The worldwide incidence of CRC in 2000 was estimated as 944,700 cases (males: 498,000; females: 446,000 cases) (1). In the United States (US) colorectal cancer accounts for approximately 11% of all cancer deaths (2). At diagnosis, 40% of the world's CRC population have metastatic or "synchronous metastases." In the US, approximately 20% of newly diagnosed patients with CRC will have synchronous metastatic cancer (3). Approximately 25% of patients with localized disease at diagnosis will ultimately develop metastatic disease. Unfortunately only a small number of patients with stage IV cancer can be cured with multimodality therapy. The majority of patients with metastatic, stage IV CRC will ultimately die of their disease (4).

Newly developed, and now standard, therapies for patients with stage IV CRC have dramatically improved survival and enhanced quality of life. Thus, in the U.S., initial therapy with combinations of 5fluorouracil (5FU) and oxaliplatin (FOLFOX) or 5FU and irinotecan (FOLFIRI) have increased response rates to approximately 45 percent (5). The addition of bevacizumab to either FOLFOX or FOLFIRI has produced response rates of 60%. Indeed, for approximately eight percent of patients with stage IV CRC, the addition of surgery to successful chemotherapy will produce a cure (6). Upon progression after so-called "first-line therapy," approximately 20% of patients will respond to a second systemic treatment combination. Most important, median survival for patients with stage IV CRC is now approaching 2.5 years (7). It is likely that with a better understanding of how to incorporate intratumoral molecular parameters such as mutations in the k-ras gene and/or quantitation of a tumor's repair genes such ERCC-1 or XRCC-1 and/or targets such as thymidylate synthase into treatment strategies, complete responses and cure rates will continue to improve.

1.1.2 First Line therapy

A series of clinical trials in the first line therapy of metastatic CRC have improved survival from a median of 12 months to nearly 24 months. A series of trial showed that combination therapy using oxaliplatin (FOLFOX4) or irinotecan (IFL or FOLFIRI) gave improved RR, OS and PFS compared with FU and LV bolus or infusion therapy. This was confirmed in the N971 US Intergroup trial showing improved RR, OS and PFS for FOLFOX compared with the control arm of IFL (5). Shortly thereafter a randomized trial of IFL with or without bevacizumab showed and improved HR for PFS and OS for the addition of the anti-VEGF antibody. This has been adopted into standard practice with all 5FU based first line therapies, including FOLFIRI or FOLFOX. A more recent study (NO16966) demonstrated

improved PFS with the addition of bevacizumab to either FOLFOX or CapeOX therapy, though of a smaller benefit due to early stopping of chemotherapy (7). As FOLFOX has become the standard first-line chemotherapy platform, particularly in the US, second line therapy has relied on irinotecan based programs.

#### 1.1.3 Second Line Therapy

A study performed by the GERCOR demonstrated that the sequence FOLFOX followed by FOLFIRI was equivalent to the reverse sequence (8). As a result, US practice has evolved to use irinotecan based regimens as second-line therapy. Either FOLFIRI or irinotecan seem equally useful in this situation and either may be used as there is no study showing a synergistic effect of fluoropyrimidines with irinotecan. In the GERCOR multi-center study, patients with advanced CRC were treated with FOLFOX followed by FOLFIRI at the time of progression or the reverse sequence. In the FOLFOX first arm, the response rate for second line FOLFIRI was 4% and PFS was 2.5 months. A larger second line study was performed to examine the role of the anti-EGF antibody, cetuximab as second line therapy on patients progressing on FOLFOX. In this 1300 patient study, the subjects were randomized to irionotecan alone or irinotecan plus cetuximab (9). The patient populations were not selected for Kras status. Again the response rate for second line irinotecan was 4.2% and PFS was 2.6 months (n = 650).

Recent reports of the predictive value of K-ras gene mutation (36,37) have demonstrated convincingly that patients with mutations in codon 12 and 13 (as determined by RT-PCR from FFPET) do not benefit from the use of anti-EGFR antibodies, either as single agent or in combination with chemotherapy programs (10). As such, two treatment tracks exist for second-line therapy, based on cetuximab use in the K-ras wild-type group and irinotecan based therapy alone in those with Kras mutations. In this study, the patient population will be limited to those with Kras wild-type status, as both arms will receive cetuximab and irinotecan.

#### 1.1.4 Biweekly Dosing of Cetuximab

Cetuximab is approved for previously treated colon cancer with nonmutated K-ras ("wild type"). The standard dose and schedule is 400 mg/m^2 loading dose x 1, then weekly 250 mg/m^2. Because of the long half-life of therapeutic monoclonal antibodies, such as cetuximab , many such agents have alternate dosing schedules of q2 weeks or even q3 weeks. In this study we have chosen the dose of 500 mg/m^2 every two weeks, for the reasons detailed below, and also to facilitate co-administration with the irinotecan (180 mg/m^2) biweekly schedule.

Data supporting the biweekly dose of cetuximab 500 mg/m^2 have been presented and published. Tabernero, et al (Tabernero, Cervantes, Martinelli, et. Al, J Clin Oncol, 24 (18 Suppl), 142s) performed a phase I/PK study demonstrating equivalent pharmacokinetic parameters for the drug on the q2w schedule. 10 patients treated on the standard dose/schedule were used in comparison. No significant differences were seen with respect to AUC, half-life, or steady-state clearance between the two schedules (Table 1). In addition, the Phase I portion of the study escalated cetuximab dose to achieve a gr 2-3 skin rash, reaching doses of 700 mg/m^2 q2w safely. The study was continuing at the time of presentation.

	Та	b	e	1
--	----	---	---	---

Schedule	C min (µg/mL)	AUC (µg/mL*h)	t 1/2 (h)	CL ss (L/h/m  )
400/250 mg/m  q1w	47.0 (37.3)	17278 (5205)	110 (24)	0.016 (0.004)
400 mg/m² q2w	25.6 (11.8)	27655 (6965)	124 (25)	0.015 (0.004)
500 mg/m² q2w	35.2 (13.8)	34953 (6275)	134 (33)	0.015 (0.003)

Mean (SD)

This combination of irinotecan 180 mg/m^2 and cetuximab 500 mg/m^2 q2w has also been reported in a Spanish phase II study (Martin-Martorell, et.al. Br J Ca 99: 455-458, 2008). Forty patients were treated and a response rate of 23% was reported (compared with 20% in the EPIC trial, N =1147), with a Disease Control Rate of 60%. Median time to progression was 3.4 months and overall survival was 8 months. This also is approximately equivalent to the cetuximab arm of the EPIC trial. Toxicity of grade 3-4 severity was reported as diarrhea = 10%, neutropenia = 7.5% and skin toxicity = 7.5%, which are all somewhat lower than similarly reported toxicity rates in the EPIC trial. In short, this phase II study suggests the activity and toxicity is not substantially different using irinotecan and cetuximab q2w compared with irinotecan every 3 weeks with weekly cetuximab. This biweekly schedule has been widely adopted in practice by US oncologists.

#### 1.2 Vascular Endothelial Growth Factor and Angiogenesis

Angiogenesis, the formation of new capillaries and blood vessels, is a tightlycontrolled, multistep process that is a component of normal physiology (including development of the embryonic vasculature, wound healing, ovulation, and menstruation). Pathologic angiogenesis contributes to tumor growth and metastasis, as well as other human diseases such as diabetic retinopathy, rheumatoid arthritis, and psoriasis (11-13). A number of growth factors have been identified as positive regulators of angiogenesis, including members of the vascular endothelial growth factor (VEGF) family, basic fibroblast growth factor, transforming growth factor alpha, transforming growth factor beta, tumor necrosis factor, platelet-derived endothelial growth factor, hepatocyte growth factor, angiogenin, interleukin-8, and placental growth factor (14,15). VEGF-A is one of several related cytokines; it is distinct in that it acts as an endothelial cell-specific mitogen and is the growth factor most consistently found in conditions associated with angiogenesis (16-19). The biological activity of VEGF-A (hereafter VEGF) is principally mediated by two structurally-related, high affinity tyrosine kinase receptors: the 180 kDa fms-like tyrosine kinase (VEGFR-1 or Flt-1) (20,21); and the 200 kDa receptor (VEGFR-2 or kinase insert domain-containing receptor [KDR]), or its murine homologue, fetal liver kinase-1 (Flk-1)(20,21). Targeted deletion of genes encoding VEGF, VEGFR-1, or VEGFR-2 in mice is lethal to the embryo, demonstrating the physiological importance of the VEGF pathway in

blood vessel formation. Mice lacking even a single VEGF allele die prior to birth due to vascular abnormalities (24,25). VEGFR-2-deficient mice have impaired blood island formation and lack mature endothelial cells (26), whereas VEGFR-1 null embryos have abundant endothelial cell-like cells, but fail to develop normal vasculature (27).

#### 1.3 The Role of VEGF and VEGFR-2 in Angiogenesis and Tumor Growth

The importance of VEGF and VEGFR-2 in angiogenesis and tumor growth has been demonstrated in several animal models. VEGFR-2 expression is associated with activated endothelium and is strongly upregulated in tumor endothelium (16,28). Inhibiting the function of the VEGF/VEGFR-2 pathway via a number of approaches, including anti-VEGF antibodies, anti-VEGFR-2 antibodies, anti-VEGF antisense ribonucleic acid expression, VEGF-based immunotoxins, soluble VEGF receptors, ribozymes to VEGF receptors, and small molecule VEGFR-2 tyrosine kinase inhibitors, has been shown to inhibit new blood vessel formation and tumor growth in a variety of animal models (29-32).

VEGF and VEGFR-2 are overexpressed in the great majority of human cancers, including carcinomas of the gastrointestinal tract, pancreas, breast, cervix, bladder, ovary, uterus, endometrium, and kidney; Kaposi's sarcoma; glioblastoma multiforme; and hemangioblastomas. In addition, messenger ribonucleic acid for both VEGFR-1 and VEGFR-2 is greatly upregulated in tumor-associated endothelial cells, but not in the vasculature of the surrounding normal tissue. A correlation between VEGFR-2 expression and tumor microvessel density has been associated with poor prognosis, advanced disease, increased risk of metastasis and recurrence, and lower relapse-free survival in patients with a variety of cancers (13,32).

Accumulating evidence suggests that the dual autocrine/paracrine mechanism also may play an important role in the growth and metastasis of certain solid tumors. For example, a VEGF/VEGFR autocrine loop was proposed as a mediator of growth and metastasis of several types of tumors, including carcinomas of prostate, ovary, pancreas, and breast; malignant pleural mesothelioma; and melanoma (32). These observations suggest that anti-VEGFR-2 antibodies may have potential as antiangiogenic and antitumor agents.

